12.9.4 Interim Analysis

No interim analysis is planned. The Data Monitoring & Ethics Committee will have

access to subgroup unblind safety data on an ongoing basis and will act in accordance with the Data Monitoring & Ethics Committee charter.

12.9.5 Analysis of Clinical Efficacy Measures

The statistical analysis will be carried out by the Junior Statistician and interpreted by the Trial Statistician, [name], who is a Senior Lecturer in Biostatistics at King's College London and co-Investigator.

12.9.5.1 Analysis of the Primary outcome

Using the ITT population we will analyse the primary outcome adjusting for baseline severity, site (stratification factor) and other key covariate information (e.g. age, gender) as reported in the SAP, using mixed effect linear models including a random effect to account for the longititininal data.

12.9.5.2 Analysis of the Secondary outcomes

We will analyse continuous outcome variables such as symptom severity and distress adjusting for baseline severity, site (stratification factor) and other key covariate information (e.g. age, gender) as reported in the SAP, using mixed effect linear models including a random effect to account for repeated measures on the same participant.

Dichotomous outcomes (e.g. proportion in clinical remission) will be analysed using logistic regression and adjusted for baseline scores and site.

Any time to event outcomes will be presented with a Kaplan Meier Plot and analyses described with a median time to event, and a log rank test.

Additionally secondary analyses will be carried out following a model building process, fitting a multivariable model for each.

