4.3 Trial Flowchart

Outcome	Screening	0	1	2	3	4
Week No.	-1 to -3	1	4	13	26	30
			(±3day)	(±7days)	(±14days)	(±7days)
Informed Consent	X					
Socio-demographic	X					
Information						
Medical History	X					
Physical examination	X	Х			Х	
(Vital Signs, ECG)						
Urine Drug Abuse		Х	Х			
Screen						

AUDIT, FTND, CEQ, SDS	X				X	
TFLB		X	X		X	
Cannabinoid levels in blood to confirm use of or abstinence from cannabis		X	X	X	X	
Pregnancy Test	Х	Х	Х	X	X	
Screening Blood Sampling- Clinical laboratory (Haematology & Biochemistry)	X				X	
Concomitant	Х	Х	X	X	X	
Medication						
Study Exclusion criteria check	X	X				
NART	Х					
Adverse Events		Х	X	X	X	X
Randomisation		Х				
Study Medication Dispensing		X	X	X		
Study Medication Compliance (pill count)			X	X	X	
Compliance Blood Sampling (Cannabidiol levels)		X	X	X	X	
Comprehensive Assessment of At-Risk Mental State	X	X	X	X	X	
Hospital Anxiety Depression Scale		X	X	X	X	
Global Functioning (Social and Role scales)		X			X	
UKU Side Effect Rating Scale		X	X	X	X	

5 Participants

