8.2.1 Primary Efficacy Parameters

Our primary efficacy parameter will be measured using the Comprehensive Assessment of At-Risk Mental States' (CAARMS)¹ (Monthly Version 2006). This is a validated instrument to rule out or confirm criteria for acute psychosis, map a range of psychopathology and functioning factors over time in young people at ultra high-risk of psychosis, and determine if an individual meets the criteria for an 'At Risk Mental State'. We will be using the English version in this population. The assessment has 7 subscales that target different areas of psychopathology and functioning: 1. Positive symptoms, 2. Cognitive change attention/concentration, 3. Emotional disturbance, 4. Negative symptoms, 5. Behavioural change, 6. Motor/physical changes, and 7. General psychopathology. Each subscale item is scored against (i) Severity (from 0 -never, absent – to 6 – extreme/psychotic/psychotic and severe –. Most items are also scored against (ii) Frequency and duration (from 0 – absent – to 6 – continuous) and (iii) Pattern of symptoms (from 0 – no relation to substance use noted – to 2 – noted only in relation to substance use). Moreover, a few items are additionally scored against (iv) Level of distress (from 0 to 100). Finally, the CAARMS includes: 8. Inclusion criteria for Group 1 Vulnerability group, Group 2 Attenuated psychosis group (CHR-APS), and Group 3 BLIPS group; 9. Psychosis threshold criterion (based on symptom severity, frequency,

and duration); and 10. Study withdrawal threshold criterion (based on Aggression/Dangerous Behaviour and/or Suicidality/Self Harm subscale severity) (Appendix 1). Within this instrument, lower scores are indicative of improved state, and higher scores of worsened state.

Primary clinical outcome: Severity of psychotic symptoms as measured using the CAARMS subscale Positive symptoms ¹. This subscale includes 4 items: 1. Unusual thought content, 2. Non-bizarre ideas, 3. Perceptual abnormalities, 4. Disorganised speech. Each subscale item is scored against (i) Severity (from 0 – never, absent – to 6 – psychotic/psychotic and severe –, (ii) Frequency and duration (from 0 – absent – to 6 – continuous), (iii) Pattern of symptoms (from 0 – no relation to substance use noted – to 2 – noted only in relation to substance use), and (iv) Level of distress (from 0 to 100). Within this instrument, lower scores are indicative of improved state, and higher scores of worsened state.

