8.2.2 Secondary Efficacy Parameters

Our secondary efficacy parameters will be measured using:

- The Comprehensive Assessment of At-Risk Mental States' (CAARMS) ¹(Monthly Version 2006). This is a validated instrument to rule out or confirm criteria for acute psychosis, map a range of psychopathology and functioning factors over time in young people at ultra high-risk of psychosis, and determine if an individual meets the criteria for an 'At Risk Mental State'. We will be using the English version in this population.

- The Hospital Anxiety and Depression Scale (HADS), an English self-assessment scale developed and found to be a reliable instrument for detecting states of depression and anxiety in the setting of an hospital medical outpatient clinic. The anxiety and depressive subscales are also valid measures of severity of the emotional disorder ⁶¹. Both the Anxiety and Depression scales range from 0 to 21, with 3 cut-offs: 0-7 = Normal; 8-10 = Borderline abnormal (borderline case); and 11-21 = Abnormal (case).

- The Social and Role Functioning scale ⁶², an English scale assessing participants' psychosocial functioning. Both the Social and Role scales range from 1 to 10, with 10 indicating superior functioning and 1 indicating extreme dysfunction. To increase reliability, both scales include focused and detailed anchor points for each rating interval. Each scale generates 3 scores: current functioning which is the lowest level of functioning in the past month, lowest and highest level of functioning reported over the past year.

Secondary clinical outcomes:

1) Distress associated with psychotic symptoms as measured using the CAARMS¹ subscale Positive symptoms – Level of distress score

2) Severity of anxiety symptoms assessed using the Hospital Anxiety and Depression Scale (HADS) ⁶¹ and level of psychosocial functioning assessed using the Social and Role Functioning scale⁶²

3) Clinical remission, as defined as no longer meeting the criteria for a diagnosis of CHR-APS

4) Total CAARMS score assessing psychopathology and functioning across all 7 CAARMS subscales

5) Change (study endpoint minus baseline) in the severity of psychotic symptoms as measured using the CAARMS between the CBD and placebo groups

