8.3 Procedures for Assessing Efficacy Parameters

Efficacy parameters will be assessed through clinical interview using standardized questionnaires/ rating instruments

8.3.1. Clinical Outcome assessment:

CAARMS psychotic symptom severity will be operationalised as in the study by Morrison and colleagues ¹² by summing the scores of product of the global rating and frequency scores of the four items of the CAARMS subscale Positive symptoms¹. CAARMS ratings will be carried out by a clinical researcher appropriately trained in administering CAARMS.

Distress associated with psychotic symptoms will be assessed by summing the Level of distress scores of the the four items of the CAARMS subscale Positive symptoms¹. Anxiety symptoms will be assessed using the Hospital Anxiety and Depression Scale (HADS) ⁶¹ Anxiety scale score.

Level of global functioning will be assessed using the Social and Role Functioning scale current functioning score ⁶².

*Clinical remission* will be defined on the basis of the CAARMS criteria ¹ as in previous studies ⁷¹. Remission requires a score of < 3 on the 'unusual thought content', 'non-bizarre ideas' and 'perceptual abnormalities' subscales and < 4 on the 'disorganized speech' subscale and a frequency scale score of < 3 over the past month.

Total CAARMS score will be operationalised by summing the scores of product of the global rating and frequency scores of all the CAARMS subscales.

In case of missing data, we will get back to the relevant study site in order to complete it.

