12.9.6 Missing Data

We anticipate very few participants withdrawing consent and expect those withdrawn to be missing at random. Since linear mixed effect modelling adjusts unbalanced designs to account for patient missing timepoint information, as long as each patient has one post-baseline outcome measure, they would be included in each analysis. However, we will explore patterns of missing data to investigate any evidence against missing at random. If there is evidence against missing at random, we will consider the impact on the analysis and may introduce imputation methods.

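### Day-182 functioning and remission get no protection from the mixed-model argument for missing data, and imputation is tied to the wrong trigger

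*Protocol*

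**What the plan says.** Section 12.9.5.2 names one model class for continuous secondary outcomes, with baseline severity and site as covariates: "using mixed effect linear models including a random effect to account for repeated measures on the same participant". Dichotomous outcomes such as remission get logistic regression adjusted for baseline scores and site. Section 8.2 sets the comparison for every endpoint at visit 3 (day 182), adjusted for baseline.

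In the flowchart (section 4.3), the row for "Global Functioning (Social and Role scales") is marked at visits 0 and 3 only. CAARMS and HADS are marked at visits 0, 1, 2 and 3.

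On missing data, section 12.9.6 argues from the mixed model: "as long as each patient has one post-baseline outcome measure, they would be included in each analysis". Patterns of missingness will be explored, and imputation may be introduced if there is evidence against missing at random (MAR).

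Two smaller passages bear on the secondary outcomes. Secondary endpoint 5 in section 8.2.2 is "Change (study endpoint minus baseline) in the severity of psychotic symptoms as measured using the CAARMS between the CBD and placebo groups". Total CAARMS is defined in section 8.3.1 as "summing the scores of product of the global rating and frequency scores of all the CAARMS subscales", whereas section 8.2.1 says "Most items are also scored against (ii) Frequency and duration".

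**The concern.** A mixed model keeps a patient who misses day 182 because the month-1 and month-3 values of the same outcome carry information about the missing one. That requires more than one post-baseline value in the model. Functioning has one, and the logistic model for remission uses one. For these outcomes the stated approach is a completer analysis at day 182.

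The rule for bringing in imputation does not repair this. It acts on evidence against MAR, but a completer analysis that leaves out earlier symptom scores can already be biased when MAR holds given those scores. Finding that loss depends on month-3 symptoms is compatible with MAR, so the rule as written would not call for imputation in the case where it helps.

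At stake are two of the clinical secondary outcomes, not the primary. Separately, a significant result on endpoint 5 could be taken as support for the primary result when it is the same test.

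**Working it through.** **1. The plan's own figure.** Section 10.2 uses an effect size of 0.4, 80% power and two-sided 0.05. The normal approximation gives n = 2 × (1.960 + 0.842)² / 0.4² = 98.1, so 99 per arm. The t-test solution is 99.08, so 100. Inflating for 32% loss: 200 / (1 − 0.32) = 294.1, so 295, against the stated 300. The figure reproduces.

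**2. Who stays in each analysis.** Schedule from section 4.3, models from section 12.9.5.2, time point from section 8.2:

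| Outcome | Visits | Post-baseline values in the stated model | Patient seen at months 1 and 3, lost before day 182 |
|---|---|---|---|
| CAARMS positive symptoms, distress | 0, 1, 2, 3 | 3 | kept |
| HADS anxiety | 0, 1, 2, 3 | 3 | kept |
| Social and Role functioning | 0, 3 | 1 | excluded |
| Remission (logistic, day 182) | CAARMS at 0, 1, 2, 3 | 1 | excluded |

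**3. What the mixed model does with one value per patient.** Var(Y) = σ²(patient) + σ²(error), and only the sum enters the likelihood. In a simulated trial of 300 the log-likelihood was −414.096 whether the patient share of the variance was set to 0, 0.25, 0.5, 0.75 or 0.99. The software still returned a fit, split the variance equally (0.4755 each) and warned that the Hessian was not positive definite. The treatment estimate was −0.341 (SE 0.114), identical to ANCOVA. The model collapses to ANCOVA in patients with a day-182 value.

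**4. How many are excluded.** At 32% loss: 300 × 0.32 = 96 excluded, 204 analysed. At the 70% completion that section 8.1 accepts as a go criterion: 300 × 0.30 = 90 excluded. How many of these have month-1 and month-3 data is not given.

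**5. Precision.** √(300/204) = 1.21 is the standard error relative to a trial with no missing data. It is not what imputation would recover; that depends on how strongly the earlier scores predict the day-182 outcome.

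**6. Bias under MAR.** Let Y be day-182 functioning, M month-3 symptoms, T arm, R = 1 if seen at day 182, and let R depend on M. Everything is conditional on baseline and site, and Y is linear in M with slope γ. Then E[Y | T, M, R = 1] = E[Y | T, M], but the completer contrast differs from the full contrast by

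γ × { (E[M | T=1, R=1] − E[M | T=1]) − (E[M | T=0, R=1] − E[M | T=0]) }.

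This is zero if M does not predict Y, or if dropout shifts the mean of M equally in both arms. If treatment changes M, the shifts will generally differ. A simulation with dropout driven by month-3 symptoms, 28% missing and assumed correlations gave about 6% attenuation of the functioning effect in completers. Imputation removed it without gaining precision.

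**7. Endpoint 5.** Write the primary model as Y = a + bT + cB + e. Subtracting baseline B gives Y − B = a + bT + (c − 1)B + e, with the same b and the same residuals. In a simulated three-visit mixed model with 32% missing at visit 3, both versions gave −0.5253 (SE 0.1321, p = 0.00007); the baseline coefficient moved from 0.503 to −0.497. Baseline-by-visit terms left the identity intact (−0.5217, SE 0.1321 for both). Change without baseline adjustment would differ (−0.448, SE 0.143), but section 8.2 adjusts every endpoint.

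**The case against.** The sentence in section 12.9.6 is conditional: it covers patients with a post-baseline value of the outcome and concerns linear mixed models. A patient without day-182 functioning does not meet the condition. That stands, so a reader who infers that the section contradicts itself goes too far; the section simply offers these two outcomes nothing.

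A reader might also infer that the functioning model cannot be fitted, or that its result would be wrong. Only the patient variance is unidentifiable, and the treatment estimate equals ANCOVA. Naming ANCOVA could fairly be left to the SAP, which is not shown.

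The 32% is the drop-out of an earlier CBT trial. The protocol plans follow-up after treatment discontinuation (sections 6.7 and 12.1), and 300 was chosen to absorb that loss: 204 still exceeds the 200 required for the primary. This answers the concern about numbers, not the concern about bias.

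Logistic regression at one time point is an ordinary choice, and imputation details are usually SAP matter. But the protocol itself states when imputation would be considered, and that condition is badly chosen.

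Endpoint 5 is openly labelled as change in the same measure and can be analysed. It is redundant, not unworkable.

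It is also tempting to call total CAARMS undefined for items without a frequency score. Section 12.1 refers to an appendix with scoring algorithms and coding of missing data, which is not shown and may settle this. No error is established.

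**Conclusion.** The point holds in a limited form. Functioning and remission are completer analyses at day 182, and the stated condition for imputation misses the MAR situation in which they can be biased. The count is 96 of 300 excluded if the planned 32% loss occurs, or 90 at the 30% that the go criterion tolerates; fewer if retention is better.

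The likely bias is modest. The 6% attenuation rests on assumed correlations and an assumed dropout mechanism that the protocol does not supply, so it is illustrative. The exclusion of patients without day-182 data and the redundancy of endpoint 5 follow from the schedule and from algebra and do not depend on simulation.

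The primary analysis is unaffected by the missing-data point, because its outcome is measured at months 1, 3 and 6. These are secondary outcomes, so the change should be made but does not put the trial's main conclusion at risk.

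**What to change.** - State that functioning is analysed by ANCOVA at day 182, adjusted for baseline and site. The treatment estimate is unchanged from the degenerate mixed model.
- Keep logistic regression for day-182 remission.
- Precede both with multiple imputation by arm, using month-1 and month-3 CAARMS and HADS as auxiliary variables. Specify it as the planned analysis under MAR, not as a response to evidence against MAR. Departures from MAR then belong in a sensitivity analysis.
- In section 12.9.6, limit the mixed-model argument to outcomes with repeated post-baseline measures.
- Label secondary endpoint 5 descriptive.
- Align the total CAARMS definition in section 8.3.1 with the scoring appendix by a cross-reference or a list of items. This is a request for clarity only.

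The cost is wording and one imputation model, with no change to visits or sample size. The imputation relies on MAR given the auxiliary scores. The expected gain is less bias; recovery of the 1.21 standard-error ratio should not be promised.

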12.9.6 Missing Data

We anticipate very few participants withdrawing consent and expect those withdrawn to be missing at random. Since linear mixed effect modelling adjusts unbalanced designs to account for patient missing timepoint information, as long as each patient has one post-baseline outcome measure, they would be included in each analysis. However, we will explore patterns of missing data to investigate any evidence against missing at random. If there is evidence against missing at random, we will consider the impact on the analysis and may introduce imputation methods.

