6.7 Withdrawal of Subjects

6.7.1 Withdrawal from study

Category of withdrawal I: As per the Declaration of Helsinki, all participants will have the right to withdraw from the study at any time without giving any reason without any prejudice to their future medical care and will be informed as such before consent. If a participant chooses to withdraw from the study, we will discuss the possibility of withdrawing from the study intervention (treatment) only and to continue their follow-up as closely as possible to the follow-up schedule defined in the protocol. They would be encouraged to not leave the study, even if they no longer wished to take the study medications. However, if a participant expresses the wish to be completely withdrawn from the study, then this view will be respected and implemented by the study team. Although not obliged to give a reason for discontinuation, a reasonable effort will be

made to establish this reason. Data already collected will be kept and included in the final analysis.

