We estimated that to have 80% power to detect a difference between CBD and placebo on symptom severity at 6 months with an effect size of 0.4, using a two-sided t-test at p=0.05, would require a sample size of n=100 per treatment arm. There was a drop-out rate of 32% reported by Morrison et al ¹². After inflating the sample size by this, we would need to recruit 300 participants for a minimum of 80% power.

10.2.2. Recruitment rate:

Out of 1980 eligible patients across all of our recruitment sites, we expect to screen a majority (around 85%) of those at each centre.

We anticipated a staggered recruitment of the sites as well as requiring three months to maximise recruitment at each site. However, by 1 year after opening our first site, we anticipated to experience our maximum consent and randsomisation rate across all sites.

At this time we anticipate a minimum of 20% (n=28, per quarter) of those screened will be randomised (See 'Plan of Investigation and timetable').

11 Assignment of interventions

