12.9.3 Population under investigation

The analyses will follow an the intention-to-treat (ITT) principle. All participants will be analysed as part of the treatment arm they were allocated to unless a participant withdraws from the study and requests all previous data to be deleted. Or a patient is randomised and does not complete any post-baseline data.

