12.9.8 Per protocol population and analysis

We will carry out a complimentary secondary analysis of the primary outcome, using the per protocol population, this will exclude the set of patients that are coded as protocol violators. These will be due to: non-compliance; non-completion of instruments within the time-windows; non-compliance with the protocol in any other way.

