12.9.10 Sensitivity analysis

The primary outcome will be re-analysed to test our assumptions. Non-compliant will be considered protocol violators and excluded from analyses.

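### The missing-data section does not address the roughly 32% loss built into the sample size, and no analysis stated in the protocol probes departures from missing at random

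*Protocol*

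**What the plan says.** **Expected loss.** Section 10.2 powers the trial for "80% power to detect a difference between CBD and placebo on symptom severity at 6 months with an effect size of 0.4", at 100 per arm. It then inflates for attrition, citing an earlier CBT trial: "There was a drop-out rate of 32% reported by" that trial. The result is 300 patients. Section 8.1 lets the trial continue if at least 70% of those due have completed six-month follow-up.

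**Missing data.** Section 12.9.6 begins: "We anticipate very few participants withdrawing consent and expect those withdrawn to be missing at random". It relies on the mixed model, which includes anyone with at least one post-baseline value, and promises to explore patterns of missingness. The next step is: "If there is evidence against missing at random, we will consider the impact on the analysis and may introduce imputation methods". Section 12.1 makes complete withdrawal from the study the only occasion on which follow-up is not collected.

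**Sensitivity analysis.** Section 12.9.10 says that the primary outcome will be re-analysed to test assumptions. The only content it then gives is: "Non-compliant will be considered protocol violators and excluded from analyses". Section 12.9.8 has already defined a per-protocol analysis of the same outcome: "this will exclude the set of patients that are coded as protocol violators". Non-compliance is the first reason it lists.

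**Data after withdrawal.** Section 6.7.1 says of a participant who leaves completely: "Data already collected will be kept and included in the final analysis". Section 12.9.3 analyses everyone as allocated "unless a participant withdraws from the study and requests all previous data to be deleted", and also leaves out randomised patients with no post-baseline data. Section 6.7.2 says that patients who progress to psychosis are then assessed for safety only, and later that their follow-up will be complete.

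**The concern.** The sample size allows for about a third of patients to have no day-182 value. The section that should deal with this speaks only of consent withdrawal, which it expects to be rare, and gives no plan for loss on the budgeted scale. Because 12.1 allows no other planned reason for not collecting follow-up, a reader of 12.9.6 would conclude that little will be missing.

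At that level of loss the primary conclusion depends on MAR. The trigger for doing more is evidence against MAR from observed patterns. Such patterns cannot separate MAR from missing not at random (MNAR), because the difference lies in values nobody has seen. If the trigger does fire, the response is optional and its method is unspecified, and standard imputation also assumes MAR. Excluding non-compliers removes patients after randomisation and says nothing about unobserved outcomes.

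The design itself gives a reason to expect outcome-related loss: on one reading of 6.7.2, efficacy assessment stops at progression to psychosis, an event closely tied to the primary symptom scale.

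**Working it through.** **1. Reproduce the sample size.** Inputs from section 10.2: effect 0.4 SD, 80% power, two-sided 5%, drop-out 32%.
- Per arm, normal approximation: 2 × (1.960 + 0.842)² / 0.4² = 98.1, so 99. The exact t-test gives 99.08, so 100, as stated.
- Inflation: 200 / (1 − 0.32) = 294.1, so 295 in total (148 per arm, 296). The stated 300 is this figure rounded up.
- Multiplying by 1.32 would give only 264, so the plan divided by the retained fraction. N = 300 therefore depends on about 32% loss. The sample size is not in error.

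**2. Translate into missing values.**
- Budgeted: 0.32 × 300 = 96 missing, 102 completers per arm, power about 0.81.
- Go/no-go tolerance: 0.30 × 300 = 90 missing.
- The few withdrawals in 12.9.6 are not quantified. If they meant 2% to 10% (assumption), 6 to 30 values would be missing, power at N = 300 would be 0.93 to 0.91, and only 205 to 223 patients would be needed.

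**3. Reliance on MAR.** Assumptions: equal loss fraction d in each arm, SD 1, two-sample standard error from completers only, and missing CBD patients worse than MAR predicts by k SD, with no shift in the placebo arm. The MAR estimate is then too favourable by d × k. An estimate of 0.40 loses significance when k = (0.40 − 1.96 × SE) / d, and the effect is zero when k = 0.40 / d.

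| Loss d | Completers per arm | SE = √(2/n) | k to lose significance | k for zero effect |
|---|---|---|---|---|
| 32% | 102 | 0.140 | (0.40 − 0.274)/0.32 = 0.39 | 1.25 |
| 30% | 105 | 0.138 | (0.40 − 0.270)/0.30 = 0.43 | 1.33 |
| 5% | 142.5 | 0.118 | (0.40 − 0.232)/0.05 = 3.4 | 8.0 |

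**4. Type I error under the same assumptions, 32% loss, no true effect.**
- k = 0.5: bias 0.32 × 0.5 = 0.16; 0.16 / 0.140 = 1.143; P(|Z + 1.143| > 1.96) = 0.21.
- k = 0.3: bias 0.096; 0.096 / 0.140 = 0.686; about 0.11.

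**5. Dependence on the assumptions.**
- With equal loss and the same k in both arms, the bias is 0.32k − 0.32k = 0.
- If baseline adjustment removed variance corresponding to a correlation of 0.5 (assumption), SE = 0.140 × √0.75 = 0.121, and the tipping point moves from 0.39 to (0.40 − 0.238)/0.32 = 0.51 SD. For a given bias, type I error would be higher.

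**6. Compare 12.9.10 with 12.9.8.** The stated exclusion in 12.9.10 is non-compliers. Section 12.9.8 excludes non-compliers, assessments outside the time windows and any other departure from the protocol. The first set lies within the second, and neither addresses unobserved outcomes.

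**The case against.** Several points on the other side stand.

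- **Withdrawal is not loss.** Section 12.9.6 speaks of consent withdrawal, which is narrower than drop-out. The 32% comes from another trial, and the 70% completion figure is a minimum, not a forecast. A reader might infer that the protocol predicts few losses in one place and many in another. Section 12.1 only partly equates the two quantities, so this is an omission in 12.9.6 and not a flat contradiction.
- **Pattern checks have a use.** They can show that missingness depends on recorded variables outside the model, such as side effects, compliance or reasons for withdrawal. Imputation with those variables is then a proper remedy. It would be wrong to call the trigger useless; what it cannot do is detect MNAR.
- **The two exclusion analyses need not coincide.** The per-protocol exclusions are wider, so 12.9.10 is contained in 12.9.8 without being identical to it.
- **A statistical analysis plan may add more.** Section 12.9 promises one before partially blinded data are summarised. A reader might infer that departures from MAR will never be examined. The protocol alone cannot support that. The point rests on the rule the protocol does state, which such a plan would have to override.
- **The illustration is one-sided.** The shifts have no source in the documents, and the standard error ignores earlier visits and baseline adjustment.
- **Data deletion is a consent matter.** A reader might infer that the exception in 12.9.3 should be struck out. The documents do not support choosing between it and 6.7.1.

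**Conclusion.** The point holds in limited form. Section 12.9.6 does not address the loss on which N = 300 depends. Its trigger cannot detect MNAR and its response is optional. The only sensitivity analysis with stated content falls within the per-protocol exclusions. No analysis stated in this protocol probes departures from MAR.

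Its size depends on the loss. At the budgeted 32%, a CBD-only departure of about 0.39 SD would remove significance from an estimate of 0.40 SD; at 5%, about 3.4 SD would be needed. Both figures assume equal loss, SD 1 and a completers-only standard error. They do not show that the result will be biased. Nothing here faults the sample size, the endpoint or the choice of primary model.

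This is a should-fix point and a cheap improvement.

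**What to change.** **Section 12.9.6.** State the budgeted loss of about 32%. Keep the MAR mixed model as primary. Make the missing-data sensitivity analysis unconditional, and keep the pattern exploration for choosing auxiliary variables.

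**Section 12.9.10.** Replace the exclusion of non-compliers, which 12.9.8 already covers, with a pre-specified delta-adjusted (tipping-point) multiple imputation of the day-182 primary outcome. Include all randomised patients, and vary the shift separately by arm, so that CBD-only and equal shifts are both shown. A reference-based imputation may be added.

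**Reconcile.** Sections 6.7.1 and 12.9.3 must agree on data already collected from participants who withdraw. The two statements in 6.7.2 on follow-up after progression to psychosis must also be reconciled, since they determine which day-182 values will exist.

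**Cost.** Wording and modest programming, with a sensitivity result that may be less favourable. The method should be fixed before anyone sees outcome data by arm.
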